#### **6.2.4. End of Study Visit**

The end of study visit will occur upon subject withdrawal from the study or upon subject completion, which will be up to 10 years or until subject has access to tafamidis for TTR-FAP via prescription. Upon regulatory approval for the treatment of TTR-FAP in their respective country and access to prescription tafamidis, subjects may be withdrawn from the study. The decision to withdraw subjects in a country will be done in consultation between the investigator and the sponsor (see Section 6.3), subject withdrawal (for any reason), or program discontinuation by the Sponsor. The following activities will be completed:

- Complete physical examination, weight and vital signs, including assessment of the following body systems: general appearance, head and neck, eyes, ears, nose, throat, respiratory, genitourinary, endocrine, cardiovascular, abdomen, skin, musculoskeletal/musculoskeletal, neurological, immunologic/allergies, hematologic/lymphatic;
- ECG;
- Urine pregnancy test (for women of childbearing potential) and determination of pregnancy;
- Assessment of ambulatory status (mPND);
- Perform NIS;
- Administer Norfolk QOL-DN;
- Determine Karnofsky Performance Scale Index;
- Ask subjects non-leading questions such as “How do you feel?” and record adverse events;
- Electrocardiogram (unless performed within 6 months prior);
- Collect blood/urine samples for laboratory assessments (Section 7.3);
- Record concomitant medications;
- Determine drug compliance and accountability.

---

In the event a subject is unable to return to the study site for the end of study visit, telephone contact with the subject approximately 30 days after the last dose of medication to assess adverse events and concomitant medications and treatments is expected. If laboratory assessments are needed to follow-up unresolved adverse events, retrieval of assessments performed at an institution local to the subject is acceptable.

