The outcome of adverse events with a date of onset during the study period should be reevaluated, and any new adverse events should be recorded. All serious adverse events, and those non-serious adverse events assessed by the investigator as possibly related to study drug should continue to be followed even after subject withdrawal from study. These adverse events should be followed until they resolve or until the investigator assesses them to be “chronic” or “stable”. Additional information on [ADVERSE EVENT REPORTING](#) can be found in Section 8.

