## **8.2. Reporting Period**

For serious adverse events, the active reporting period to Pfizer or its designated representative begins from the time that the subject provides informed consent, which is obtained prior to the subject's participation in the study, ie, prior to undergoing any study-related procedure and/or receiving investigational product, through and including 28 calendar days after the last administration of the investigational product. Should an investigator be made aware of any SAE occurring any time after the active reporting period, it must be promptly reported.

- Adverse events (serious and non-serious) should be recorded on the CRF from the time the subject has taken at least one dose of study treatment through last subject visit.

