6.2.5. Death

Time to death will be calculated from the first dose of the treatment (either Fx-005 or Fx1A-201), from active treatment start, and from onset of symptom, respectively. Subjects alive at the end of the study will be censored at the last visit date. For subjects who have received a liver and/or heart transplant, time will be censored at the time of transplant. Death after discontinuation will be censored at time of discontinuation. The date of onset of symptom is the start date of the earliest symptom related to ATTR in the Medical History CRF.

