6.4. Discontinuations

All reasons for discontinuation will be summarized including: discontinuations due to adverse events, discontinuations due to laboratory abnormalities, discontinuations due to

death, discontinuations due to liver and/or heart transplant, discontinuations due to other causes (not laboratory abnormalities, death or liver transplant), and all cause discontinuation.

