8.1.3. Analyses for Time to Event Endpoints

Kaplan-Meier estimates will be computed for all time to event endpoints, including median, interquartile ranges, and 95% confidence intervals. Kaplan-Meier curves will be presented at yearly intervals. These analyses will be provided by treatment group and by TTR mutation. Separate analyses will be conducted using both measurements of baseline, at study start and at active treatment start as specified above. Additionally, a set of analyses will be done for the time from onset of symptom.

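### A death soon after a non-fatal exit is a fatal SAE but a censored observation in the SAP's survival curve; label the rule and add a sensitivity analysis

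*SAP*

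**What the plan says.** SAP 6.2.5 measures time to death from three origins: first dose in Fx-005 or Fx1A-201, start of active treatment, and symptom onset. Subjects alive at the end are censored at their last visit and transplant recipients at transplant. For the rest the rule is "Death after discontinuation will be censored at time of discontinuation". SAP 8.1.3 applies Kaplan-Meier estimation to all time-to-event endpoints and adds: "These analyses will be provided by treatment group and by TTR mutation".

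The protocol collects deaths beyond exit:

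- Section 8.2 keeps active SAE reporting open "through and including 28 calendar days after the last administration of the investigational product", and section 8.5 makes an event that results in death an SAE.
- Section 6.2.4 says that SAEs "should continue to be followed even after subject withdrawal from study". For a subject who cannot attend the end of study visit, it expects "telephone contact with the subject approximately 30 days after the last dose of medication to assess adverse events".
- CRF recording is shorter. Under section 8.2, adverse events "should be recorded on the CRF from the time the subject has taken at least one dose of study treatment through last subject visit".

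Exit for a non-fatal reason is foreseen. Protocol 6.3 lists adverse event and death as separate withdrawal reasons, and SAP 6.4 summarises "discontinuations due to adverse events" apart from discontinuations due to death.

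**The concern.** The safety report and the survival curve can disagree about the same patient. A subject who leaves because of an adverse event and dies of it days later is reported as a fatal SAE, but enters the curve as alive and censored on the day of exit. Nothing readable in SAP 7 or 8.1.3 brings that death back as an event.

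Kaplan-Meier estimation assumes that censored subjects carry the same risk as those who stay. Protocol 8.3 counts worsening of the underlying disease as an adverse event, so an adverse-event exit can mark a deteriorating patient. If so, the censoring is informative and the error favours the drug. The study is descriptive (SAP 4.1), so the displayed curve is itself the result, and SAP 3 foresees interim reporting to scientific meetings and for regulatory purposes.

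**Working it through.** The plan gives no death rate, event count or survival figure, so there is nothing of its own to reproduce.

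**1. The rule applied to one subject.** Suppose exit and last dose both fall on day 1000.

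| Day of death | SAP 6.2.5 | Protocol 8.2 |
|---|---|---|
| 1000 | event on day 1000 | fatal SAE |
| 1001, 1010 or 1028 | censored on day 1000 | fatal SAE inside the window |
| 1029 | censored on day 1000 | outside the active window |

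The 28 days run from the last dose. A subject who stopped drug before leaving the study therefore has a shorter window after exit.

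**2. Effect of one reclassified death.** At that date the curve drops by S/n (S = survival just before, n = number at risk). Censoring can only increase this, so the minimum is 1/N0, with N0 the starting group size. Protocol Table 1 shows 65 tafamidis and 63 placebo patients in Fx-005, which caps the two groups.

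- Tafamidis-Tafamidis: at least 1/65 = 1.5 points
- Placebo-Tafamidis: at least 1/63 = 1.6 points
- Illustration later in follow-up, S = 0.90 and n = 30: 0.90/30 = 3.0 points

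The documents do not give the size of the non-V30M group.

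**3. Expected bias under assumed rates.** None of these rates is in the documents: death hazard h = 0.05 to 0.10 per year; non-death exit hazard c = 0.03 to 0.05 per year; hazard k × h for w = 28/365.25 years after exit; last dose on the day of exit.

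- SAP rule: mortality at T = 1 − exp(−hT)
- 28-day rule: hazard(t) = (h·on + h·k·win)/(on + win), integrated to T, where on = exp(−(h+c)t) and win = the integral of c·exp(−(h+c)s)·exp(−hk(t−s)) over s from max(t−w, 0) to t

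The horizon depends on the time origin. Fx-006 completers already have 30 months of study medication (Protocol 1.2.2) and had to complete Fx-006 to enrol. They cannot die in or leave this study during those months. Year 5 from first dose in Fx-005 therefore has at most 5 − 2.5 = 2.5 years at risk. Five years at risk corresponds to year 7.5 from that origin.

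Mortality in percent, SAP rule then 28-day rule:

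| T (years at risk) | c | h | SAP rule | k=1 | k=5 | k=10 | k=20 |
|---|---|---|---|---|---|---|---|
| 2.5 | 0.03 | 0.05 | 11.75 | 11.75 | 11.85 | 11.97 | 12.21 |
| 2.5 | 0.05 | 0.10 | 22.12 | 22.12 | 22.41 | 22.76 | 23.41 |
| 5 | 0.03 | 0.05 | 22.12 | 22.12 | 22.30 | 22.51 | 22.93 |
| 5 | 0.05 | 0.10 | 39.35 | 39.35 | 39.80 | 40.34 | 41.35 |

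These rows are the ends of the range. The differences are 0.0 points at k=1. At k = 5, 10 and 20 they are 0.1-0.3, 0.2-0.6 and 0.5-1.3 over 2.5 years, and 0.2-0.5, 0.4-1.0 and 0.8-2.0 over 5 years.

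**4. Expected number of reclassified deaths in a group of 65.** Exits = 65 × c/(h+c) × (1 − exp(−(h+c)T)), multiplied by (1 − exp(−hkw)). For T=5, c=0.05, h=0.10, k=20: 11.43 × 0.142 = 1.63. The chance of at least one is 1 − exp(−expected).

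| T | k=5 | k=10 | k=20 |
|---|---|---|---|
| 2.5 | 0.08-0.25 (8-22%) | 0.17-0.50 (15-39%) | 0.33-0.96 (28-62%) |
| 5 | 0.15-0.43 (14-35%) | 0.30-0.84 (26-57%) | 0.59-1.63 (45-80%) |

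**The case against.** The two sections serve different purposes. Protocol 8.2 sets a safety-reporting window and SAP 6.2.5 a censoring rule; neither document ties the survival curve to 28 days. A reader might infer that the SAP contradicts the protocol, or that the rule is wrong and must be replaced. The documents do not support that. Stopping follow-up at exit is a defensible on-study choice, and it fits the censoring at last observation in SAP 7. It also avoids an asymmetry: deaths after exit can arrive through SAE reports, while the call at about 30 days applies only to subjects who cannot attend the end of study visit. Those who attend have no required day-28 contact. This stands, and it is why the rule should remain the main analysis.

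A reader might also infer that survival is overstated as a matter of fact. That does not follow. The bias is zero if risk is unchanged after exit. The multipliers 5, 10 and 20 have no basis in the documents, and the calculation applies them to all non-death exits, although raised risk is not evident in subjects who leave for prescription access.

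Nor can the plan be faulted for leaving discontinuation undefined or for lacking a deaths table. The appendices are largely redacted and the table list is a separate addendum. The mismatch arises whether discontinuation means last dose or study exit.

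Finally, the stakes are limited: no hypothesis is tested, and time to death is not among the endpoints in Protocol 2.2. That lowers the priority. It does not explain why known deaths should drop out of a survival display without comment.

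**Conclusion.** The point holds in a limited form. Deaths within 28 days of the last dose, after exit for another reason, are collected as fatal SAEs but cannot be events in the survival analysis. Deaths that are themselves the exit reason still count, and transplant recipients have their own rule, so the affected group is narrow. Whether the curve is biased depends on short-term risk after exit, which is plausibly raised for adverse-event exits but is not documented.

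The certain part is the step of at least 1.5 to 1.6 points per reclassified death in the two Fx-005 treatment groups. The expected bias is illustrative only: from nil up to 1.3 points over 2.5 years at risk, or 2.0 points over 5 years, at the most extreme assumed rates and multiplier. This justifies a sensitivity analysis and a transparent account of deaths. It does not justify changing the main analysis.

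**What to change.** In SAP 6.2.5 and 8.1.3:

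1. Keep the current rule as the main analysis and label it on-study survival with censoring at discontinuation.
2. Add one sensitivity Kaplan-Meier analysis that counts deaths through 28 days after the last dose on their own date. Censor other discontinued subjects at last dose + 28 days if known alive, otherwise at last contact.
3. Take these deaths from SAE reports reconciled with the CRF, because CRF recording of adverse events stops at the last subject visit.
4. Tabulate all known deaths by timing (on drug, within 28 days, later, post-transplant) and by exit reason, unless the tables addendum already does so.
5. Keep censoring at transplant.

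The cost is SAP wording, one reconciliation, one extra analysis and one table, with no new visits. Survival may look slightly less favourable. Where day-28 vital status is unknown, counting late deaths while censoring survivors at exit biases mortality upwards. In simulation under the same assumed rates this is about 0.04-0.12 points at 5 years at risk.

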6.3. Adverse Events

Treatment emergent adverse events will be summarized by all causes and treatment relatedness groupings. For the purposes of this study, treatment emergent is defined as an event which begins after enrollment in the current study (B3461023) or which worsens during the course of the current study. In addition, severity of the adverse events will be summarized by all causes and treatment relatedness.

6.4. Discontinuations

All reasons for discontinuation will be summarized including: discontinuations due to adverse events, discontinuations due to laboratory abnormalities, discontinuations due to

death, discontinuations due to liver and/or heart transplant, discontinuations due to other causes (not laboratory abnormalities, death or liver transplant), and all cause discontinuation.

6.5. Covariates

Due to the small number of subjects and the descriptive nature of this study, baseline will be used as a covariate in the change from baseline models and where appropriate, gender. TTR mutations will be categorized as V30M or nonV30M and all analyses will be done separately by these TTR mutation groupings.

6.6. Baseline

The baseline for all measures will be the last measurement prior to the first dose of study drug in study Fx-005 or Fx1A-201. For the V30M subjects, an additional set of analyses will be performed using a second baseline, the last measurement prior to active treatment from study Fx-005 or Fx-006.

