**Study Design:**

This is a Phase 3, open-label study designed to obtain additional, long-term, open-label safety and efficacy data for tafamidis and to continue to provide subjects with 20 mg oral tafamidis (soft gel capsule) who have completed either Protocol Fx-006 (a 1-year, open-label extension study to Protocol Fx-005 which is a randomized, double-blind, placebo-controlled, 18-month study to evaluate the safety and efficacy of tafamidis) or Protocol Fx1A-201 (a Phase 2, open-label study to evaluate TTR stabilization as well as the safety and tolerability of tafamidis) up to 10 years or until subject has access to tafamidis for TTR-FAP via prescription. Upon regulatory approval for the treatment of TTR-FAP in their respective country and access to prescription tafamidis, subjects may be withdrawn from the study. The decision to withdraw subjects in a country will be done in consultation between the investigator and the sponsor.

Subjects who successfully complete Protocol Fx-006 or Fx1A-201 will report to the clinical unit on Day 0 (Baseline) to sign the informed consent form and determine their eligibility for Protocol Fx1A-303/B3461023. In addition, on Day 0 (Baseline), subjects will have their entrance criteria reviewed, medical history and demography for all subjects will be obtained. Relevant end of study assessments from Protocols Fx1A-201 and Fx-006 will serve as Baseline assessments for Protocol Fx1A-303/B3461023 if these examinations were performed within 30 days of Day 0 (Baseline). For any subject successfully completing Protocol Fx-006, the Karnofsky Performance Scale Index will be assessed and the cranial nerve and upper limb components of the NIS will be performed and combined with the NIS-LL data from the end of study visit from Protocol Fx-006.

If there is more than 30 days between the final study visit of Fx-006 or Fx1A-201 and Day 0 (Baseline) of Fx1A-303/B3461023, all Day 0 study procedures will be performed (ie, no data from the final study visits from the previous studies will be utilized).

[figure not shown]
Eligible subjects will begin once-daily dosing with 20 mg tafamidis at home on Day 1 (ie, first dose) and will return to the clinical unit for study visits every 6 months.

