### **1.2.2. Study Rationale**

This current study is being conducted to obtain additional safety and efficacy data and to provide continued dosing of tafamidis for up to 10 years, or until subject has access to tafamidis for TTR-FAP via prescription, to patients with TTR-FAP who have not undergone liver or heart transplantation and who have completed either Protocol Fx-006 (EudraCT

---

2008-001262-87) or Protocol Fx1A-201 (EudraCT 2007-006791-12), as described above. Upon regulatory approval for the treatment of TTR-FAP in their respective country and access to prescription tafamidis, subjects may be withdrawn from the study. The decision to withdraw subjects in a country will be done in consultation between the investigator and the sponsor (see Section 6.3). Subjects will continue to receive once-daily 20 mg tafamidis. Safety will be assessed via the incidence of treatment-emergent AEs, the use of concomitant medications, and by results from clinical laboratory testing, physical examinations, ECGs, and vital signs.

Prior to enrollment in this current study, subjects who complete Protocol Fx-006 will have received study medication for a total of 30 months (18 months of double-blinded treatment in Protocol Fx-005 plus 12 months of open-label treatment in Protocol Fx-006); subjects who complete Protocol Fx1A-201 will have received open-label tafamidis for 12 months.

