## **9.1. Sample Size Determination**

There is no formal sample size calculation for this protocol. Subjects who completed Protocols Fx-006 and Fx1A-201 are eligible for this study; up to 110 subjects are expected to enroll in Protocol Fx1A-303/B3461023.

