4. HYPOTHESES AND DECISION RULES

4.1. Statistical Hypotheses

This study is descriptive in nature, and as such, there are no formal hypotheses to be tested.

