8.3. Safety Analyses

Safety data will be summarized for the safety analysis population.

Treatment and Disposition of Subjects: Subject evaluation groups will show end of study subject disposition and will show which subjects were analyzed for efficacy, as well as for safety (adverse events and laboratory data). Frequency counts will be supplied for subject discontinuation(s) by treatment.

A listing of treatment duration for each subject will be reported in accordance with the sponsor reporting standards.

Demographic and Baseline Characteristics. A break-down of demographic data will be provided for age, gender, race, weight, body mass index, and height. Each will be summarized by treatment group, sex at birth and 'All Subjects' in accordance with the sponsor reporting standards. All baseline and disease characteristics will also be summarized.

Discontinuations. Subject discontinuations due to adverse events will be detailed and summarized.

Adverse events (AEs): Treatment emergent adverse events will be summarized by causality and severity.

Hematology, Biochemistry and Urinalysis: Descriptive statistics will be provided for each test result and for change from baseline by visit. Additional summaries for abnormalities in laboratory measures will be provided for the following populations: without regard to baseline, abnormal at baseline and normal at baseline.

Baseline is defined in two ways as described above.

ECG: Changes from baseline (defined as the last evaluation prior to the first dose of study drug) will be summarized for each of the ECG measures listed above. In addition, ECG changes from baseline will be categorized as follows:

- a change from baseline \geq 60 msec,
- a change from baseline \geq 90 msec;
- a change from baseline between 30 msec (inclusive) and $<$ 60 msec;
- a reading of greater than 450 msec at any visit;
- a reading of greater than 480 msec at any visit;
- a reading of greater than 500 msec at any visit.

Baseline is defined in two ways as described above.

Note: In Italy only Echocardiograms and Holter Monitoring were performed, and therefore, the Italian subjects will not be included in these summaries.

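### The SAP defines only parent-study baselines: no change from entry into this study with a confidence interval is specified, and NIS Total is dropped for V30M although Day 0 supplies it

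*SAP*

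**What the plan says.** The protocol uses Baseline for Day 0 of this study in its Study Design summary, Schedule of Activities and sections 6.1, 7.1 and 7.5. Values from the last parent-study visit may stand in: "Relevant end of study assessments from Protocols Fx1A-201 and Fx-006 will serve as Baseline assessments for Protocol Fx1A-303/B3461023", provided they were taken within 30 days. The protocol also covers a longer gap ("If there is more than 30 days between the final study visit of Fx-006 or Fx1A-201 and Day 0 (Baseline) of Fx1A-303/B3461023"), in which case every Day 0 procedure is done afresh.

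SAP 6.6 sets a different reference: "The baseline for all measures will be the last measurement prior to the first dose of study drug in study Fx-005 or Fx1A-201". For V30M subjects it adds that "an additional set of analyses will be performed using a second baseline, the last measurement prior to active treatment from study Fx-005 or Fx-006". Neither is Day 0.

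On earlier exposure, protocol 1.2.2 says that "subjects who complete Protocol Fx-006 will have received study medication for a total of 30 months", made up of 18 months in Fx-005 and 12 in Fx-006. Fx1A-201 completers have had 12 months. SAP 8.3 says "All baseline and disease characteristics will also be summarized" and gives no separate definition of baseline for that table.

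**The concern.** The first objective is additional long-term data from this study. A reader of the report will want to know how ill subjects were when they entered and what happened to them afterwards. Under SAP 6.6 every change from baseline combines parent-study change with on-study change, and the characteristics table describes measured disease status before the parent study began.

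The two documents also use one word for different time points, so a table headed change from baseline can be misread. The safety tables show the same split. SAP 6.3 counts treatment-emergent events from enrollment in this study, while the vital-sign and weight flags in SAP 8.3 run from the 6.6 baselines. A weight loss of 7% that happened wholly in a parent study could be flagged at an on-study visit.

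**Working it through.** **1. The plan's own figure.** Fx-005 plus Fx-006 = 18 + 12 = 30 months, which agrees with protocol 1.2.2.

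**2. Nominal age of each SAP baseline at entry, and share of the elapsed interval that precedes this study.** Share = age / (age + study month).

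| Group and SAP reference | Age at entry (months) | Month 12 | Month 24 |
|---|---|---|---|
| V30M, first baseline, both groups | 30 | 30/42 = 71% | 30/54 = 56% |
| Tafamidis-Tafamidis, second baseline | 30 | 30/42 = 71% | 30/54 = 56% |
| Placebo-Tafamidis, second baseline | 12 | 12/24 = 50% | 12/36 = 33% |
| Non-V30M (Fx1A-201), first baseline | 12 | 12/24 = 50% | 12/36 = 33% |

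These ages are nominal, not ceilings, because no upper limit on the gap before Day 0 is stated. Assumed gaps of 1, 3 or 6 months turn 30 into 31, 33 or 36, and 12 into 13, 15 or 18. With a Day 0 reference the age is 0 to 30 days.

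**3. Can on-study change be recovered from the planned output?** If LSMeans are reported for the entry time point and for a later month, their difference is a point estimate of on-study change. Its interval is not recoverable, because it depends on the correlation ρ between the two LSMeans. With equal standard errors (an assumption), SE(difference) / SE(one LSMean) = √(2(1 − ρ)):

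- ρ = 0: 1.41
- ρ = 0.5: 1.00
- ρ = 0.8: 0.63
- ρ = 0.9: 0.45

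The documents give no ρ. Across this range the interval width varies about threefold (1.41/0.45 = 3.1).

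**4. NIS Total and NIS-UL.** Side by side:

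- Protocol 6.1 has the cranial-nerve and upper-limb parts done on Day 0 for Fx-006 completers and joined to the lower-limb score, so a full NIS exists at entry.
- Protocol 9.2.3 plans a mixed model of change from Baseline in NIS using this protocol and Fx1A-201 only. For Fx-006 completers the first full NIS under that plan is the Day 0 one.
- SAP 6.1 omits NIS Total and NIS-UL for V30M because the parent studies did not collect the full score.

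The omission follows from the choice of baseline. A Day 0 value is available.

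**5. Karnofsky.** Protocol 6.1 has it assessed on Day 0 for Fx-006 completers, with no carry-over from Fx-006. SAP 8.2 applies the change-from-baseline methods of 8.1.1 to it. The documents do not say whether Fx-005 collected it. If it did not, V30M subjects have no reference value on the first baseline.

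**6. What Day 0 cannot serve.** The Schedule of Activities shows no laboratory sample, ECG or mPND in the Day 0 column, so Day 0 could not be the baseline for all measures.

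**The case against.** The case for leaving the SAP alone is substantial. Protocol 9.2.2 and 9.2.4 put parent-study data into change from Baseline for NIS-LL and Norfolk QOL-DN, which makes most sense if the baseline precedes those studies. SAP 8.2 describes its efficacy endpoints as cumulative. Protocol 9 allows the SAP to modify the plans. The study tests nothing ("This study is descriptive in nature, and as such, there are no formal hypotheses to be tested") and has no target precision ("There is no formal sample size calculation for this protocol"). All of this stands, and it makes the difference an unreconciled definition, not a breach of the protocol.

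A reader might infer that nothing at all is reported about change during the study, or that severity at entry is invisible. The documents do not support either. Treatment-emergent events run from enrollment, vital signs are summarized at each visit, the protocol summarizes NIS-LL and Norfolk at each scheduled assessment, ambulation has shift tables, and demographics are collected on Day 0. Several SAP appendices are redacted and the table lists sit in a separate addendum, so a Day 0 table there cannot be excluded.

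A reader might also infer that the parent baseline costs precision. Take an illustrative model with correlation 0.5 between parent and on-study slopes, slope SD s per year and measurement SD e. The variance of the Month 12 change is 9.75s² + 2e² from the parent baseline and s² + 2e² from Day 0. For (s, e) = (1.5, 2), (2, 3) and (3, 3) the SE ratios are 1.71, 1.61 and 1.98. But these compare a 42-month change with a 12-month change, using inputs that the documents do not give. Under constant progression the longer change is 42/12 = 3.5 times as large, so its relative precision is better. The ratios show no defect.

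Finally, Day 0 does not give a clean group comparison. SAP 8.1.1 notes that misaligned schedules prevent comparing change on active treatment after the parent trials. Day 0 does align the visits, but prior tafamidis exposure then differs (nominally 30 against 12 months) and both groups are selected for completing two studies.

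**Conclusion.** The point holds in a limited form. Both SAP baselines are appropriate for the cumulative question and should stay. What is missing from the readable SAP is a change from study entry with a confidence interval, although 95% intervals are the SAP's stated way of summarizing data (SAP 4.2). Measured baseline characteristics nominally predate entry by 30 or 12 months, depending on group and reference, plus any gap before Day 0. The clearest cost is the loss of NIS Total and NIS-UL for V30M subjects, a planned analysis of the first-listed efficacy endpoint.

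The conclusion rests on reading SAP 6.6 as written, for all measures, and on the redacted appendices and separate table list containing no Day 0 rule. It is a worthwhile, inexpensive improvement to a descriptive plan. It does not invalidate the planned analyses.

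**What to change.** Keep both existing baselines. In SAP 6.6 add Day 0 of B3461023, including parent end-of-study values taken within 30 days, as a supplementary reference labelled as on-drug. Then:

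- Apply it to NIS-LL, NIS Total and NIS-UL (V30M included), TQOL and its domains, Karnofsky, weight and BMI, and vital signs. Exclude laboratory tests, ECG and mPND, which have no Day 0 assessment in the schedule.
- Present change from Day 0 with 95% confidence intervals by on-study month, separately for V30M and non-V30M.
- Note beside the V30M tables that prior tafamidis exposure is nominally 30 months for Tafamidis-Tafamidis and 12 for Placebo-Tafamidis, so the group contrast is not randomised.
- Add a Day 0 column to the baseline and disease characteristics table.
- Name the reference point in each table title, and amend SAP 6.1 so that it agrees with protocol 9.2.3 on NIS.

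The cost is SAP wording and one further set of tables from data already collected. The drawback is more output and a reference value measured on treatment, which the label must make plain.
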